4.1.2 Analysis of OLE Treatment

The following variables collected at baseline will be summarized for the OLE population. No treatment comparisons will be made since GA29145 is a single-arm open-label study.

For continuous variables, descriptive statistics including n, mean, median, standard deviation, minimum, and maximum will be calculated. For categorical variables, number and percentage in each category will be displayed.

Demography

- Age
- Age category (≥ 18 to < 40 , ≥ 40 to < 65 , ≥ 65)
- Sex
- Race
- Ethnicity
- Region
- Smoking status history
- Body mass index
- Weight

Disease Characteristics

- Duration of disease (years)
- Duration of disease (years) category (< 3 , ≥ 3 to < 8 , ≥ 8)
- Disease location (Ileum only, Colon only, Ileum + Colon)
- Number of affected ileo-colonic segments
- Ulcerations at baseline
- Mean SF score
- Mean AP score (4-point scale)
- CDAI score
- CDAI Category (≤ 330 , > 330) (IxRS and Rave)
- SES-CD score
- CD-PRO/SS – Functional score

- CD-PRO/SS – Bowel score
- Inflammatory Bowel Disease Questionnaire (IBDQ) total score
- Fecal calprotectin ($\mu\text{g/g}$)
- Fecal calprotectin category ($<250 \mu\text{g/g}$, $\geq 250 < 500 \mu\text{g/g}$, $\geq 500 \mu\text{g/g}$)
- C-reactive protein (CRP) levels (mg/L)
- CRP category ($\leq 2.87 \text{ mg/L}$, $> 2.87 \text{ to } \leq 10 \text{ mg/L}$, $> 10 \text{ mg/L}$)
- Albumin

Baseline Treatments

- Use of oral CS at Baseline (yes vs. no) (IxRS and Rave)
- Use of IS at Baseline (yes vs. no) (IxRS and Rave)
- Prior anti-TNF exposure (yes vs. no) (IxRS and Rave)

The patients with prior anti-TNF exposure at baseline will be further evaluated to include the number of TNFs previously received and status (e.g., primary non-responder, secondary non-responder, Intolerant, etc).

4.1.3 Primary Efficacy Analysis

To evaluate the efficacy of etrolizumab during long-term open-label treatment, efficacy will be summarized within the population of patients who enroll into the Study GA29145. Both endoscopic improvement and clinical remission will be summarized in two separate analyses. Due to the open-label nature of the study, no treatment comparisons will be made.

Concerning missing data and treatment withdrawal imputation, there will be 3 strategies employed, described below.

Hybrid LOCF

Within this strategy, at each visit only patients who had the possibility of reaching the visit will be considered in the analysis for that specified visit. Patients will be deemed evaluable at a visit if it was possible for them to have reached this visit based on their enrollment date and the date of the closure of Part 1 of the study.

- Patients for whom it is not possible to have reached the visit at the time of the clinical cut off are termed non-evaluable and will not be included in the analysis at that visit.
- For evaluable patients with missing data, Last Observation Carried Forward (LOCF) will be used from their most recent available data.

- For evaluable patients who previously withdrew from treatment, they will be imputed as a non-responder until their maximum hypothetical visit (i.e., the maximum visit that they could have attended if they had remained within the study).
 - For visits after a patient's maximum hypothetical evaluable visit, they will be removed from the analysis.

As Observed

Within this analysis only the available data at each visit will be summarized. No imputation will be performed for missing data or treatment withdrawals.

Non-Responder

Within this strategy, at each visit only patients who had the possibility of reaching the visit will be considered in the analysis for that specified visit. Patients will be deemed evaluable at a visit if it was possible for them to have reached this visit based on their enrollment date and the date of the closure of Part 1 of the study.

- Patients for whom it is not possible to have reached the visit at the time of the clinical cut off are termed non-evaluable and will not be included in the analysis at that visit.
- Evaluable patients with missing data will be set as a non-responder.
- For evaluable patients who previously withdrew from treatment, they will be imputed as a non-responder until their maximum hypothetical visit (i.e., the maximum visit that they could have attended if they had remained within the program).
 - For visits after a patient's maximum hypothetical evaluable visit, they will be removed from the analysis.

Maximum Hypothetical Evaluable Visit

A patient's maximum hypothetical study day (i.e., the maximum visit that they could have attended if they had remained within the study) is calculated as follows:

Maximum hypothetical study day = (15th May 2022 - Patient's Day 1 OLE enrollment date)

For the hybrid LOCF analysis and non-responder analyses, this will impute patients who have withdrawn as a non-responder until the 15th May 2022, which was the latest day of dosing reported in the closure of the study announcement. This excludes patients who withdrew from study drug with reason being stated as "study terminated by sponsor" after 15th February 2022, these patients will not be imputed as non-responders and will be considered 'treatment completers' for the efficacy analysis with data included "as observed".

Simple Endoscopic Score for Crohn's disease (SES-CD) score: Handling of Partially Available Segments

Note that in the OLE study GA29145, no central adjudication took place and therefore only a local score will be available for the Week 108 assessment. This differs from Study GA29144, which utilized central adjudication and up to 3 readers provided a score. To overcome differences in reader availability between studies the following approach will be used:

Baseline score will utilize data from all available readers with adjudication applied to determine the final total SES-CD score. This aligns with the original Day 1 Baseline score in study GA29144 and ensures that the central readers are retained in the Baseline score derivation, as reported in the CSR analysis.

The determination of segment availability will use the Local reader only for both the baseline and post-baseline time points, as follows:

- any segment(s) missing by the local reader at baseline will not be considered in the Week 108 visit total SES-CD total score calculation
- any segments(s) available at baseline that are not available at Week 108 will result in a non-responder status for the patient for endoscopic improvement/remission. For continuous data the patient's baseline segment score will be carried forward (BOCF) to impute the Week 104 segment score when calculating the total SES-CD score.

4.1.3.1 Endoscopic Improvement and Remission at Week 108

As endoscopy data is only collected at a common time point of Week 108 during the OLE Study GA29145, the endpoints of endoscopic improvement and endoscopic remission will be summarized only at this time point. These endpoints will be examined overall and separated by their previous endoscopic improvement status at their latest visit prior to enrollment into GA29145 i.e., at the parent study's (GA29144) Week 14 or Week 66.

The handling of patients with partially available segments is detailed in Section [4.1.3](#), this is not considered as true missing data.

Population: All patients who enrolled into Part 1 of the OLE Study GA29145.

Baseline: The original baseline value from the parent study will be used to calculate improvement.

Sub-groups:

- All patients overall and split by prior endoscopic improvement status and their prior aTNF exposure status.

Analysis 1 - Non-Responder

Missing data: Patients who are non-evaluable at Week 108 (i.e., could not have reached the maximum visit if they had remained within the program as detailed in Section 4.1.3) will be removed from the analysis. Patients who remain in Study GA29145 but are missing endoscopy scores (i.e., the assessment was not done) will be imputed as non-responders within the analysis, as LOCF is not appropriate when endoscopy data is not collected routinely.

Intercurrent events: Patients who withdraw during Study GA29145 will be set to non-responders using the composite strategy if they could have reached OLE Week 108 at the time of the clinical cut-off date had they not withdrawn from treatment. This excludes patients who withdrew from study drug on or after 15th February 2022.

Analysis 2 - As Observed

Missing data: If a patient has missing data at a visit, they will be removed from the analysis and no imputation will be performed.

Intercurrent events: No imputation will be performed for treatment withdrawals

4.1.3.2 Simple Endoscopic Score for Crohn's disease (SES-CD) score at Week 108

As endoscopy data is only collected at a common time point of Week 108 during the OLE Study GA21945, continuous SES-CD score will be summarized only at this time point and at parent study Baseline. The handling of patients with partially available segments is detailed in Section 4.1.3, this is not considered as true missing data.

Population: All patients who enrolled into Part 1 of the OLE Study GA29145.

Baseline: The original baseline value from the parent study will be used as the baseline SES-CD score.

Analysis 1 - BOCF

Missing data: If a patient has missing data at a visit (i.e., the assessment was not done), they will be removed from the analysis and no imputation will be performed.

Intercurrent events: No imputation will be performed for treatment withdrawals

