- ⁱ For women of childbearing potential, including those who have had a tubal ligation. Perform a urine pregnancy test; if the urine pregnancy test result is positive, perform a confirmatory serum pregnancy test. Pregnancy test will be carried out at home once the patient starts etrolizumab administration at home. Pregnancy test must be completed prior to etrolizumab administration. Patient is to report the pregnancy test result in the patient diary. Patients must be instructed at screening and reminded throughout the study that in case of a positive pregnancy test, they should stop self-administration of study drug and call the site immediately. Do not administer etrolizumab unless the serum pregnancy test result is negative.
- ^j CDAI, SF, and AP scores will not be recalculated at the Week 0 visit; however, scores from the most recent visit in Study GA29144 (Week 10, Week 14, Week 74, or Early Withdrawal visit) should be entered into the database along with date of assessment.
- ^k Patients are to complete the patient diary for stool frequency, abdominal pain, and general well-being for 10 days prior to the clinic visits when CDAI assessments are scheduled (every 12 weeks).
- ^l PML neurologic examination consists of the PML Subjective Checklist and the PML Objective Checklist. Administered by a qualified HCP before other assessments, as per [Appendix 8](#).
- ^m The ileocolonoscopy should be conducted on the day of the clinic visit or within 10 days after the clinic visit was completed.
- ⁿ An ileocolonoscopy will be performed at the Week 108 visit or early withdrawal visit if prior to Week 108. If early withdrawal visit occurs after the Week 108 visit, then the ileocolonoscopy with biopsies should be conducted only at Week 108.
- ^o Includes hemoglobin, hematocrit, platelet count, RBC count, mean corpuscular hemoglobin, mean corpuscular volume, mean corpuscular hemoglobin concentration, red cell distribution width, WBC count, and differential.
- ^p Not required if unscheduled visit leads to withdrawal and assessment previously conducted at unscheduled visit.

Appendix 1
Open-Label Extension (OLE, Part 1) Schedule of Assessments (cont.)

- ^q Includes sodium, potassium, chloride, bicarbonate, glucose, blood urea nitrogen, creatinine, calcium, phosphorus, magnesium, total and direct bilirubin, total protein, albumin, aspartate aminotransferase, alanine aminotransferase, lactate dehydrogenase, alkaline phosphatase, creatine phosphokinase, and uric acid.

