4.1.3.3 CDAI Remission and Clinical Remission Every 12 Weeks

The percentage of patients in CDAI remission or clinical remission as defined in the Efficacy Derivations Section 1.3.1 will be summarized for each OLE visit for patients who entered Study GA29145. All OLE visits will be summarized until a minimum of 20 evaluable patients overall remain within the analysis (i.e., an evaluable patient either reached the visit or could have reached the visit if they had remained within the OLE).

Population: Patients who enroll into Part 1 of Study GA29145.

Baseline: The original baseline value from the parent study will be used to calculate remission, where applicable.

Sub-groups:

- Table outputs: All patients overall, split by aTNF exposure status and by OLE Day 1 CDAI remission or clinical remission status, as appropriate.
- Figure outputs: All patients overall and split by OLE Day 1 CDAI remission or clinical remission status.

Analysis 1 - Hybrid LOCF

Missing data: If patients who remain in Study GA29145 at the specified visit are missing data then LOCF will be used to impute. For visits where patients are non-evaluable (i.e. it is not possible for them to have reached the specified visit at the time of the clinical cut-off date) they will be removed from the analysis.

Intercurrent Events: Using the composite strategy in the case where patients have withdrawn from the Study GA29145, they will be set to non-responders for all visits where they are evaluable. This excludes patients who withdrew from study drug with reason being stated as “study terminated by sponsor” after 15th February 2022.

Analysis 2 - As Observed

Missing data: If a patient has missing data at a visit, they will be removed from the analysis and no imputation will be performed.

Intercurrent events: No imputation will be performed for treatment withdrawals

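### For 12-weekly CDAI and clinical remission, neither planned analysis counts a missed on-study assessment as non-remission, and Hybrid LOCF may carry a score measured before the first OLE dose

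*SAP*

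**What the plan says.** SAP 4.1.3 announces a set of rules for missing data and withdrawal: "Concerning missing data and treatment withdrawal imputation, there will be 3 strategies employed, described below". They are Hybrid LOCF, As Observed and Non-Responder. For a patient who could have reached the visit but has no data there, Hybrid LOCF says: "For evaluable patients with missing data, Last Observation Carried Forward (LOCF) will be used from their most recent available data". Non-Responder says: "Evaluable patients with missing data will be set as a non-responder". Both are worded visit by visit, and both count earlier treatment withdrawals as non-response up to the last visit the patient could have attended. Patients whose drug was stopped by the sponsor's termination after 15 February 2022 are exempt and enter as observed.

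SAP 4.1.3.3 then assigns two of the three to the 12-weekly remission endpoints. Analysis 1 is Hybrid LOCF: "If patients who remain in Study GA29145 at the specified visit are missing data then LOCF will be used to impute". Analysis 2 is As Observed: "If a patient has missing data at a visit, they will be removed from the analysis and no imputation will be performed". Non-Responder is not listed there. Its only use is in SAP 4.1.3.1, for endoscopic improvement and remission at Week 108, where patients without an endoscopy "will be imputed as non-responders within the analysis, as LOCF is not appropriate when endoscopy data is not collected routinely".

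On the earliest score available to carry, Protocol Appendix 1 (footnote j) says: "CDAI, SF, and AP scores will not be recalculated at the Week 0 visit". The most recent parent-study scores are entered instead. SAP 4.4, on changes to planned analyses, covers only anti-therapeutic antibodies.

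**The concern.** CDAI and clinical remission are the only efficacy outcomes measured repeatedly in the OLE, so they carry the evidence on long-term efficacy. Each needs a patient diary kept for 10 days before the visit, and CDAI also needs hematocrit, weight and physician items. A patient can therefore attend, be dosed and still have no usable score.

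When that happens, Hybrid LOCF gives the patient the last known status, however old, and As Observed leaves the patient out. Neither shows the rate if the missed assessments were not remissions. The strategy that would show it is already written for repeated visits, yet it is applied only to an endpoint with a single common time point.

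The second issue is where the carried value comes from. A patient who misses Week 12 may be given a parent-study score. A measurement taken before any OLE dose would then count as remission during the OLE.

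**Working it through.** The plan states no remission rate, missing-data rate or target for this analysis, so there is no figure to reproduce. The check has two parts: tracing which strategy each endpoint gets, and sizing the difference.

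**1. Strategy by endpoint**

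| Endpoint | Analyses planned | Missed assessment, patient still on study |
|---|---|---|
| Endoscopic improvement and remission, Week 108 (SAP 4.1.3.1) | Non-Responder; As Observed | Non-response; dropped |
| SES-CD score, Week 108 (SAP 4.1.3.2) | One, labelled BOCF | Dropped |
| CDAI and clinical remission, every 12 weeks (SAP 4.1.3.3) | Hybrid LOCF; As Observed | Last value; dropped |

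The last row contains no analysis in which a missed assessment counts as non-remission.

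**2. Formulas at one visit**

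Among evaluable patients, let:
- w = share withdrawn (non-responders under both imputation strategies);
- m = share on study with a missed assessment;
- p = remission rate among those assessed;
- q = share of the missed patients whose last value was remission.

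Then:
- As Observed = p
- Hybrid LOCF = (1 − w − m)p + mq
- Non-Responder = (1 − w − m)p
- Hybrid LOCF − Non-Responder = mq

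Since mq cannot be negative, Hybrid LOCF is never the lower of the two. They agree only if nobody missed the visit (m = 0) or no missed patient was last seen in remission (q = 0).

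**3. Gap in percentage points (m and q are assumptions)**

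| m | q = 0.4 | q = 0.7 |
|---|---|---|
| 5% | 5 × 0.4 = 2.0 | 5 × 0.7 = 3.5 |
| 10% | 10 × 0.4 = 4.0 | 10 × 0.7 = 7.0 |
| 20% | 20 × 0.4 = 8.0 | 20 × 0.7 = 14.0 |

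**4. Worked example (all inputs assumed)**

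Take w = 40%, m = 10% and p = q = 0.7. Per 100 evaluable patients, 50 are assessed and 10 are missed.
- As Observed: 35/50 = 70.0%
- Hybrid LOCF: (35 + 7)/100 = 42.0%
- Non-Responder: 35/100 = 35.0%

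**5. Two places where it matters most**

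- *Day 1 remitters at Week 12.* SAP 4.1.3.3 splits results by OLE Day 1 remission status. If Week 0 values may be carried, every Day 1 remitter who misses Week 12 is counted as still in remission. Then q = 1 and the gap is the whole missed share, for example 10 points at m = 10%.
- *Late visits.* Visits are reported down to 20 evaluable patients. There, one carried remission moves the rate by 1/20 = 5 points.

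**The case against.** The strongest case against the point has five parts.

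- **The gap to Non-Responder is not LOCF error.** Let t be the true remission share among missed patients. Hybrid LOCF is off by m(q − t) and Non-Responder by −mt. If q = t = 0.7 and m = 10%, Hybrid LOCF is exact and Non-Responder is 7.0 points too low. LOCF also carries non-remission. This stands in full. A reader might infer that the plan inflates the remission rate; the documents do not support that, because they say nothing about the true status of missed patients.
- **A near lower bound can be pieced together.** As Observed remitters over the Hybrid LOCF denominator give 35/100 = 35.0% in the example, and the difference in remitter counts (42 − 35 = 7) is the number of carried remissions. Protocol Section 6 promises counts as well as proportions. This largely stands, so it would be wrong to say the report offers no bound. The reader must still construct it, and it does not show how many carried values predate the OLE.
- **The assignment was deliberate.** SAP 4.1.3 says: "Both endoscopic improvement and clinical remission will be summarized in two separate analyses". SAP 4.1.3.1 explains why LOCF is unsuitable for endoscopy, while CDAI is collected routinely. That justifies LOCF as a main analysis for remission. It does not explain omitting a sensitivity analysis already defined in visit-by-visit terms.
- **Other rules restrain the carry.** Withdrawal turns the patient into a non-responder, visits the patient could not have reached are dropped, and missed scheduled visits are a listed possible reason for discontinuation (Protocol 4.5.1). A reader might picture one old remission carried for years. The wording permits that, but nothing in the documents shows it is common.
- **The Week 0 issue is narrow.** Protocol 4.4.4 designates final parent-visit data as first-visit OLE data, a parent score can be carried only until the first OLE assessment, and patients entering after worsening or relapse would usually carry non-remission. All true. Patients who completed the Maintenance Phase, or finished Week 14 after it closed to entry, may enter in remission, and they are the ones affected.

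**Conclusion.** The point holds as a gap in sensitivity analysis and in the definition of the carried value, not as a demonstrated bias. For CDAI and clinical remission, neither planned analysis counts a missed on-study assessment as non-remission, and the Hybrid LOCF wording lets a pre-OLE score count as OLE remission.

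The excess of Hybrid LOCF over Non-Responder is mq. The range of 2 to 14 points rests wholly on the assumed 5-20% missed and 0.4-0.7 last seen in remission, and it is zero if no missed patient was last seen in remission. Apart from the sponsor-termination exception, withdrawals are already treated as failures, so the issue is confined to patients who stay on study.

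The study is single-arm and descriptive and will have a synoptic report with limited efficacy data. No error rate is affected, only how the remission rates are read. This is a cheap improvement rather than an essential correction.

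**What to change.** 1. In SAP 4.1.3.3, add an Analysis 3 (Non-Responder) for CDAI and clinical remission, as defined in SAP 4.1.3. Label it a sensitivity analysis and keep the sponsor-termination exception.
2. In Hybrid LOCF, carry forward only values measured after the first OLE dose. Treat an evaluable patient with no such value as a non-responder, again keeping the sponsor-termination exception.
3. Report the number of carried-forward values at each visit.

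A maximum carry length is optional. The documents give no basis for a particular limit, so it is for the sponsor to set.

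The cost is a few lines of SAP text and one more run of an existing program, with no new data collection. The downside is a slightly lower reported remission rate: Analysis 3 can only equal or fall below Hybrid LOCF, and item 2 can only lower early-visit rates or leave them unchanged.

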4.4.4.3 Crohn's Disease Activity Assessments

Disease severity will be evaluated using the CDAI, SF, AP, and SES-CD, which are described below.

Crohn's Disease Activity Index

The CDAI quantifies the signs and symptoms of patients with CD (see [Appendix 5](#)). The CDAI consists of eight factors; each factor is summed after adjustment with a weighting factor (Best et al. 1979). The components of the CDAI include number of liquid or soft stools, abdominal pain, general well-being, presence of complications, use of Lomotil[®] (diphenoxylate/atropine) or other opiates for diarrhea, presence of an abdominal mass, hematocrit, and percentage deviation from standard weight. Of the eight factors of the CDAI, three are patient reported (number of liquid or soft stools, abdominal pain, and general well-being), four are based on physician assessment (presence of complications, use of Lomotil[®] or other opiates for diarrhea, presence of abdominal mass, and percentage of deviation from standard weight, which is based on the patient's weight at the visit), and one factor is based on a blood test (hematocrit). Patients are to report their abdominal pain severity, loose-stool frequency, and general well-being for 10 days prior to each study visit on a patient diary. The weighted sum of the average scores over 7 days is calculated for the PRO component of the CDAI score. The Bristol Stool Scale is provided to patients as a reference for determining loose stools (see [Appendix 7](#)).

Stool Frequency and Abdominal Pain

Two patient reported factors will be evaluated: the frequency of liquid or soft stools and abdominal pain. A mean daily score will be calculated for each factor, where the average will be taken over 7 days prior to the assessment visit. Patients are to report their loose-stool frequency (the Bristol Stool Scale will be provided) and abdominal pain severity for 10 days prior to each study visit on a patient diary.

Simple Endoscopic Score for Crohn's Disease (SES-CD)

The SES-CD is assessed by the investigator through endoscopy and is a composite of four factors (ulcer size, percentage of ulcerated surface, percentage of surface affected by other lesions, and extent of stenosis) in up to five ileocolonic segments (see [Appendix 11](#) for further details) and will be entered into the RAVE eCRF. Unlike the parent study, GA29144, there will be no central adjudication performed; only the investigator's evaluation of SES-CD will be used.

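### The Week 108 SES-CD comparison sets a multi-reader adjudicated baseline against a local-only score, so a systematic reader offset would be counted as endoscopic change

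*SAP*

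**What the plan says.** SAP 4.1.3, under the handling of partially available SES-CD segments, describes two reading methods. For the extension, "no central adjudication took place and therefore only a local score will be available for the Week 108 assessment". For the parent study, "This differs from Study GA29144, which utilized central adjudication and up to 3 readers provided a score". Protocol 4.4.4.3 agrees about the extension: "there will be no central adjudication performed; only the investigator's evaluation of SES-CD will be used".

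The SAP then sets out how it will deal with this. For the baseline, "Baseline score will utilize data from all available readers with adjudication applied to determine the final total SES-CD score". For segments, "The determination of segment availability will use the Local reader only for both the baseline and post-baseline time points". The reason given for the adjudicated baseline is consistency with the Day 1 score already reported for GA29144.

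SAP 4.1.3.1 applies that baseline to the binary endpoint: "The original baseline value from the parent study will be used to calculate improvement". SAP 4.1.3.2 uses the same parent-study value as the baseline for the continuous score. Change in SES-CD from GA29144 Week 0 to Week 108 or early withdrawal is an exploratory outcome in Protocol 3.3.4 and SAP 1.3.3.

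**The concern.** The segment rule makes the two totals cover comparable bowel. It does not make them the same kind of measurement. A patient with all five segments scored by every reader on both occasions still has an adjudicated multi-reader total at Week 0 and one investigator's total at Week 108. Reader type and time point are therefore completely confounded.

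If local readers tend to score lower or higher than the adjudicated result, that tendency appears as healing or as lack of it. The study has one arm (SAP 4.1.2: "No treatment comparisons will be made since GA29145 is a single-arm open-label study"), so no control group carries the same offset and cancels it. Neither document plans a local-to-local analysis, a central re-read of Week 108, a reader-agreement table or a statement of the limitation. Yet SAP 4.1.3 uses the local reader's baseline segments to decide availability, so local baseline reads should already be held.

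What is at stake is the interpretation of the Week 108 endoscopic results, which SAP 4.1.3 places under its primary efficacy heading.

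**Working it through.** The plan has no figure to reproduce: the study is descriptive, with no sample size calculation, test or alpha. The check is an identity followed by an illustration.

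**Step 1: the identity.** With every segment scored both times, write L for the local score and A for the adjudicated score.

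Reported change = L(W108) - A(W0) = [L(W108) - L(W0)] + [L(W0) - A(W0)]

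The first bracket is change as seen by local reading. The second is purely a reader difference at Week 0, and nothing in SAP 4.1.3 removes it. If its mean is d points, the mean change moves by d.

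**Step 2: which outcomes it reaches.**

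| Outcome | Uses the baseline score? | Affected by the mismatch? |
|---|---|---|
| SES-CD change, Week 0 to Week 108 | Yes | Yes, by d on the mean |
| Endoscopic improvement | Yes (SAP 4.1.3.1) | Where a patient crosses the cut-off |
| SES-CD at or below 4 (2 for ileal patients), no subcategory score above 1 | No | No, though it rests on a local read |

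**Step 3: illustration of size.** The documents give no reader-agreement data and do not define the improvement cut-off, so every input here is assumed:

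- Adjudicated baseline B: gamma-distributed, mean 13, SD 6, rounded, minimum 3, maximum 60.
- Week 108 score T on the same scale: B x (1 - r + e), with r the true mean reduction and e Normal with SD 0.35, rounded and limited to 0-60.
- Local Week 108 score: T + d, limited to 0-60.
- Improvement: Week 108 score no more than 0.5 x B.
- 300,000 simulated patients.

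| Offset d (points) | Improved, r = 0 | Improved, r = 30% |
|---|---|---|
| -3 | 30.7% | 60.9% |
| -2 | 22.1% | 51.5% |
| -1 | 14.4% | 41.1% |
| 0 | 8.7% | 30.7% |
| +1 | 5.2% | 22.0% |
| +2 | 3.1% | 15.4% |
| +3 | 1.9% | 10.6% |

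The offset's contribution is the difference from the zero row. At d = -1 it is 14.4 - 8.7 = 5.7 percentage points with no true change, and 41.1 - 30.7 = 10.4 points with a 30% true reduction. At d = +1 it is 5.2 - 8.7 = -3.5 and 22.0 - 30.7 = -8.7 points.

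**Step 4: random disagreement only.** With d = 0 and reader disagreement of SD 2, the mean change moves by at most 0.05 points. Improvement moves from 8.7% to 12.1% (r = 0) and from 30.7% to 33.0% (r = 30%).

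**Step 5: what a local-to-local comparison does.** For the change score, a constant offset cancels: (T + d) - (B + d) = T - B, apart from floor effects at zero. For a 50% rule it cancels only partly, because T + d <= 0.5(B + d) is the same as T + d/2 <= 0.5B. So d = -2 read locally both times gives the mixed-reader result for d = -1, which is 14.4% (r = 0), against 22.1% for the planned comparison and 8.7% on the adjudicated scale throughout. The two derivations are therefore best shown together, with the Week 0 difference beside them.

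**The case against.** The strongest reply is that the SAP made a disclosed and reasoned choice. It says that the readers differ, keeps the central readers in the baseline and preserves agreement with the GA29144 report. It also splits Week 108 results by parent-study improvement status, which a local baseline might not match. This stands: it justifies keeping the adjudicated analysis and tells against replacing it. It does not make the mixed-reader difference interpretable.

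Three stronger readings are tempting.

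- **A reader might infer that every reader difference is reported as improvement or worsening.** It is not. Only a systematic offset moves the mean appreciably, only differences that cross the cut-off alter the binary result, and no worsening category exists.
- **A reader might infer that an investigator who knows the treatment will score low, so the results flatter the drug.** Knowledge of treatment follows from the open-label design and investigator scoring, but the documents give no direction or size for any resulting bias. The adjudicated baseline draws on all available readers, so the local read may already be in it, which would shrink the offset.
- **A reader might infer that local-to-local scoring cures the problem.** It does not remove open-label expectation at Week 108: Week 0 was read in a placebo-controlled study and Week 108 was not. Nor do the documents say that the same person read both examinations.

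The consequences are also limited. There are no tests or treatment comparisons, the CSR is synoptic with limited efficacy data (SAP 4), and endoscopic appearance at Week 108 is an exploratory objective, although SES-CD score is also a listed efficacy outcome.

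**Conclusion.** The concern holds in a limited form. The planned comparison mixes reader types, and the stated approach aligns segments but not scores. A systematic Week 0 local-minus-adjudicated offset passes one-for-one into SES-CD change and shifts the improvement proportion through patients near the cut-off. No planned output can show how much of the result this is.

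The size in this study is unknown. The identity needs no assumption beyond complete segments. The percentages rest entirely on assumed values for the baseline distribution, variability, cut-off and offset; they show sensitivity and do not estimate bias. The effect on improvement also assumes that it is defined relative to baseline, as SAP 4.1.3.1 implies without giving the definition. The absolute SES-CD outcome is outside this point. No test, alpha or sample size is affected, so this is a cheap improvement to a descriptive analysis rather than a flaw that invalidates it.

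**What to change.** Keep the adjudicated-baseline analysis, for consistency with GA29144, and make three additions.

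1. In SAP 4.1.3.1 and 4.1.3.2, add a side-by-side derivation of endoscopic improvement and SES-CD change that uses the local Week 0 score against the local Week 108 score, with the existing segment rules.
2. Tabulate the local-minus-adjudicated SES-CD difference at Week 0 in OLE patients, so that the offset is measured rather than guessed.
3. State in the CSR that the local-to-local version removes the reader-type difference but not open-label expectation at Week 108.

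The cost is SAP wording, one extra derivation and one table from data that should already be held. The downside is a second baseline figure that will not match the GA29144 report, which a footnote can explain.
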